14.5 Additional Analyses of Primary and Secondary Endpoints

A number of additional analyses is planned to evaluate the relationship between the primary and selected secondary/exploratory endpoints:

- Relationships between selected continuous endpoints, i.e. UMSARS total score and subdomains, MRI, blood/CSF NfL, α-synuclein, COMPASS-S/SC, CGI-S, PGI-S, SE-ADL, gait parameters and EQ-5D-5L VAS will be explored using scatterplots for both absolute values and change from baseline.
- The minimal clinically important difference within-patient (MCID) on each scale will be investigated. Further details on the work identifying the MCID will be described in a specific separate *Psychometric SAP*. The outcome of the MCID analysis will be reported in a separate report.

14.6 Analysis of Exploratory Endpoints

For exploratory endpoints the following methodology will be applied:

- For continuous exploratory endpoints, a MMRM will be applied for observed data (OC), using observed data from the Withdrawal Visit for patients dropping out (for other reasons than death), if available. The model will contain the following effects: baseline score, treatment, visit, CCI, Region, treatment*visit and baseline score*visit as fixed effects and subject as random effect. The main comparison will be at Week 48. Initially, an unstructured covariance matrix will be fitted. In case of issues converging, a Toeplitz structure will be used.
- Time-to-event exploratory endpoints up to EoTDB will be analysed applying a Cox proportional-hazards model.

- Number of falls per individual according to the sensor-based PAMSys device will be analysed descriptively including data from the pre-defined periods only.
- Target engagement and biofluid markers in general will primarily be explored graphically. If applicable, relevant efficacy endpoints will be evaluated especially for patients obtaining target engagement.
- The analysis of Screening and Exit semi-structured, qualitative interviews will be prespecified in a specific Qualitative Analysis Plan (QAP). Whenever a combined quantitative and qualitative approach is considered, a dedicated Mixed Method QAP will be developed.

Open-label extension (OLE)

• All continuous endpoints following treatment extension will primarily be analysed descriptively. In addition, a MMRM will be applied similar to the one described above to the change from the original baseline (DB baseline), where patients originally treated with pbo will be kept as a separate group. No formal testing will be applied.

15 Testing Strategy

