## 10.2.1.10 PAMSys

At US sites, patients will have the option for undergoing objective sensor-based assessments, which will be performed during 5 distinct intervals (2 weeks interval between randomization and baseline, then 4 periods of 4 weeks) (hereafter referred to as the "Sensor subset"). Patients can withdraw from these additional assessments without having to withdraw from the main study. Patients may consent to participate in one or both of the objective sensor-based assessments. The use of the sensor does not apply to a patient who scores 4 on UMSARS Part I item 7 (walking) or if the patient is wheelchair bound for unrelated disorders. This needs to be evaluated at each visit, where the sensor is to be dispensed.

BioSensics' PAMSys is a system that consists of a wearable motion sensor that is paired to a tablet. The wearable sensor is worn as a pendant on the chest for continuous monitoring of falls and physical activity. The tablet supports electronic COA technology, which, when a fall is detected by a sensor, asks the patient to confirm or deny the occurrence of the detected fall. Patients receive the sensor during the scheduled visits and are instructed to wear the sensor continuously for 30 days at each interval and bring the sensor back at the next scheduled visit.

The parameters provided by the PAMSys system are: number of detected falls, posture classification (sitting, standing, walking and lying down), number of steps, and compliance for wearing the sensor.

Detailed instructions on how to administer PAMSys system will be provided to the site in a Rater Guideline.

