4.5 Exploratory Endpoints

4.5.1 Double-Blind Period

Disease progression

• as assessed by longitudinal changes from baseline in the abbreviated UMSARS (aUMSARS) score up to EoTDB

Function

• Changes from baseline to Week 48 in aUMSARS

Autonomic symptoms

• Change from baseline to Week 48 in heart rate, blood pressure, and orthostatic symptoms, as assessed in UMSARS Part III

Disease milestones

- Time to wheelchair use, as assessed by the recording of wheelchair use in the physical examination CRF Form
- Change from baseline to Week 48 in frequency of falls, as assessed by PamSys device
- Change from baseline to Week 48 in gait parameters, as assessed by FeetMe device

MRI biomarkers

- Percentage change from baseline to Week 48 in cerebral blood flow in ROIs; putamen and cerebellum, as measured by arterial spin labelling (ASL) MRI
- Percentage change from baseline to Week 48 in tissue integrity in ROIs; primary ROIs: putamen, cerebellar cortex and white matter; secondary ROIs: caudate nucleus, globus pallidus and middle cerebellar peduncle, as measured by diffusion-tensor imaging (DTI) MRI

Blood/CSF biomarkers

- CSF: Change from baseline up to Week 48 in t-tau and NfL concentrations
- CSF: Concentrations of 'free' and 'total' α-synuclein at baseline and Week 48
- CSF: Changes from baseline up to Week 48 in pathological species of α-synuclein
- Blood: Plasma concentrations of 'free' and 'total' α-synuclein during treatment and safety follow-up

4.5.2 **Open-label Extension Period**

Effect on long-term treatment:

- Change from baseline of the DBP and baseline of the OLE to End-of-Treatment of the OLE (EoTOLE) in UMSARS TS and mUMSARS score
- Change from baseline of the DBP and baseline of the OLE to EoTOLE in CGI-S score
- Change from baseline of the DBP and baseline of the OLE to EoTOLE in PGI-S score
- Change from baseline of the DBP and baseline of the OLE to EoTOLE in SE-ADL score
- Change from baseline of the DBP and baseline of the OLE to EoTOLE in health-related quality of life, as assessed using EQ-5D-5L score
- Percentage change from baseline of the DBP and baseline of the EoTOLE in brain atrophy in ROIs, as measured using vMRI
- Change from baseline of the DBP and baseline of the OLE to EoTOLE in blood NfL concentrations

5 Analysis Sets

The patients will be assigned to analysis sets based on IMP intake and post-baseline assessments of the primary efficacy variable in the Treatment Period.

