For both Baseline and the DB-Period, compliance is evaluated as number of days used for each of the two wearables, i.e., FeetMe and PanSys, which will be summarized within each interval where applied and treatment group. Furthermore, the number of patients missing 7 days or more and 14 days or more in a 28-day period will be presented by interval and treatment group. The following intervals will be evaluated:

- BL interval: V2 to V3 (2 weeks)
- Interval 1: V7 to V9 (4 weeks)
- Interval 2: V10 to V11 (4 weeks)
- Interval 3: V13 to V14 (4 weeks)
- Interval 4: V17 to V18 (4 weeks)

Records outside the above predefined intervals will be included as long as they can be mapped to one of the above intervals according to the defined visit windows (See section 24.2). Individual wearable data will be mapped to the end visit defining each interval, corresponding to the visit where the wearable is handed back.

The summaries will be based on the SBS.

13 Primary Estimand

The following primary estimand is defined as:

Proposed handling of IE's

For evaluating the appropriateness of this overall strategy, a number of sensitivity analyses will be performed using different imputation strategies for missing data. For additional information see section 14.3.5: Sensitivity Analyses of the Primary Endpoint, also covering sensitivity analyses for the key Secondary Endpoint.

Key Secondary Estimand

A key secondary study estimand will be defined in a similar manner with the endpoint of interest being the CCI

14 Efficacy

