24.1.10 BioSensics[™] PAMSys sensor

PAMSys (Physical activity and posture) is a clinical-grade wearable sensor for continuous remote monitoring of physical activity, sleep, posture, gait parameters and falls, which will be applied periodically for a subgroup according to study procedure (See Appendix IV).

Panel 13 below contains a list of available parameters and endpoint description.

Posture and postural transition	Gait parameters
 Posture classification (sitting, standing, walking and lying down) Postural transition (duration and number of occurrence) Sedentary behavior 	 Number of steps (for example per hour) Walking duration (for example per hour) Time stamp of individual steps Cadence Cadence variability Number of episodes of walking (for example per day) Number of steps per walking episode
Sleep and sleep quality	Falls and fall risk
 Start- and end-time of periods of lying down Sleep onset latency (i.e., time lying down before sleep onset) Wake time after sleep onset Total sleep time 	 Falls (number of falls and time of occurrence) Continuous fall risk monitoring

Panel 13 Derivation of PAMSys parameters

In case of large amount of missing data for a subject within a given period, endpoints might not be derived according to BioSensics procedure and hence the data will be set to missing. Data cleaning and classification will take place prior to database lock.

Additionally, raw data will be made available as sdtm format.

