Within each dispense/observation period (BL, V9, V12, V15, and V18) the defined visit windows will be applied to identify valid data entries. Within each period, the total number of falls will be calculated as the sum of the Q2 responses. In addition, an adjusted total number of falls per period will be calculated as the total number of falls divided by the number of days where the Fall Diary was filled out (Q1 NOT missing). The adjusted number of falls per period will be the primary endpoint for further analysis of falls.

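### SAP 14.6 gives no denominator for PAMSys falls, although the endpoint is change in fall frequency from a 2-week baseline interval to a 4-week interval at Week 48

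*SAP*

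**What the plan says.** **Endpoint.** SAP 4.5.1 lists, among the exploratory endpoints, "Change from baseline to Week 48 in frequency of falls, as assessed by PamSys device".

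**Analysis.** SAP 14.6 states: "Number of falls per individual according to the sensor-based PAMSys device will be analysed descriptively including data from the pre-defined periods only". The protocol (17.9.7) had planned a negative binomial model for the same falls. It named no exposure offset.

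**Derivation.** Panel 13 in SAP 24.1.10 lists the sensor's available fall output as "Falls (number of falls and time of occurrence", together with continuous fall-risk monitoring. For some other outputs, such as steps and walking episodes, the same panel suggests a unit of time. For falls it does not. Below the panel, the SAP says that endpoints may not be derived, and will then be set to missing, when much of a period's data is absent. It gives no numeric cut-off.

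**Observation time.** SAP section 12 gives "BL interval: V2 to V3 (2 weeks") and "Interval 4: V17 to V18 (4 weeks"). Protocol 10.2.1.10 agrees: a 2-week interval between randomization "and baseline, then 4 periods of 4 weeks". The same protocol section also tells patients to "wear the sensor continuously for 30 days at each interval".

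**Fall diary.** The diary has the same 2-week and 4-week periods. SAP 24.1.11 derives a total per period and also an adjusted value, "calculated as the total number of falls divided by the number of days where the Fall Diary was filled out", and makes the adjusted value primary for the analysis of falls. SAP 24.2.7 carries the diary's visit-window approach over to the devices, but not this adjustment.

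**The concern.** A change from baseline in frequency needs the two ends measured on the same time base. Here the planned observation time doubles between baseline and Week 48, and the only quantity named for analysis is a count. If the programmer follows SAP 14.6 literally, the change mixes how often patients fall with how long they were observed. The summary would show apparent worsening in both arms even with no worsening, and it could hide a real improvement.

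The SAP deals with the same difference in period length for the diary, so its silence for the sensor is probably an oversight rather than a choice. At stake is whether the sensor result can be read as the endpoint it is meant to express.

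**Working it through.** **Inputs**
- Nominal visit weeks (Protocol Panel 2): V2 = -2, V3 = 0, V17 = 44, V18 = 48.
- Fall rate: not given in the documents. I assume a constant 0.5 to 3.5 falls per week. The ratio below does not depend on this choice.
- Wear: full, unless stated otherwise.

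**Step 1: reproduce the planned interval lengths**
- Baseline: 0 - (-2) = 2 weeks = 14 days.
- Week 48: 48 - 44 = 4 weeks = 28 days.

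Both agree with SAP section 12. The other three intervals in that section also come to 4 weeks each.

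**Step 2: expected count for an unchanged rate**

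Count = rate per week x weeks observed.

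| Assumed falls per week | Baseline (x 2) | Week 48 (x 4) | Apparent change |
|---|---|---|---|
| 0.5 | 1 | 2 | +1 |
| 1 | 2 | 4 | +2 |
| 2 | 4 | 8 | +4 |
| 3.5 | 7 | 14 | +7 |

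The ratio is 28/14 = 2.0 at every rate.

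**Step 3: a real change in rate**

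Count ratio = 2 x true rate ratio.
- True halving: 2 x 0.5 = 1.0, which reads as no change.
- True 40% reduction: 2 x 0.6 = 1.2, which reads as a 20% rise.

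**Step 4: departures from nominal lengths**
- If 30 days are worn after baseline and 14 at baseline: 30/14 = 2.14.
- With the ±3 days of Panel 21 at both ends, baseline runs from 14 - 6 = 8 to 14 + 6 = 20 days, and Week 48 from 28 - 6 = 22 to 28 + 6 = 34 days. The extreme ratios are 22/20 = 1.1 and 34/8 = 4.25.

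So 2.0 is the nominal figure, and individual patients can lie well to either side of it.

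**Step 5: comparison between arms**
- Week 48 counts: both arms have 28 planned days, so interval length alone causes no bias.
- Change from baseline with stable rates: 4r - 2r = 2r. If the arms differ at baseline, say 1.0 and 1.5 falls per week, the changes are +2 and +3. That is a difference of 1 fall although neither arm changed.

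**Step 6: partial wear**

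A stable patient at 1 fall per week who wears the sensor for 14 of 28 days at Week 48 has 2 falls against 2 at baseline, a change of 0. This matters only if the period is not set to missing under SAP 24.1.10, and without a cut-off that cannot be determined.

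**Step 7: after the fix**

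At 1 fall per week, 2/14 = 0.143 per day at baseline and 4/28 = 0.143 per day at Week 48. The ratio is 1.0 and the change is 0.

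**The case against.** The best reply is that the SAP is silent here rather than wrong. The endpoint is called a frequency, which is compatible with a rate. Panel 13 lists what the device can supply, not the final analysis variable, and SAP 24.7 says the vendor will already have derived the relevant parameters for each period. A reader might infer that the SAP prescribes an unadjusted count, or rules out division by days worn. It does neither, and the vendor's specification is not among the documents. This stands: the accurate statement is that no denominator is specified. It does not remove the problem, because the only quantity named for analysis is a count, and where a rate was wanted, for the diary, the SAP wrote it out.

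Three other strong readings also go too far:
- **Bias between arms.** Planned interval lengths are the same in both arms. Unequal wear between arms is possible but not shown, and section 12 reports days used by interval and treatment group, so a reader would see it.
- **No comparison with the diary.** SAP 24.1.11 also derives the unadjusted diary total, and the baseline and Week 48 intervals match, so counts can be set against counts. What is missing is a sensor value on the diary's primary scale.
- **Partial wear certain to distort.** The missing-data rule in SAP 24.1.10 may remove such periods.

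On size, high assumed rates make the absolute changes look large. Before Protocol Version 4.0, falling more than once a week at screening was an exclusion (Protocol 6.3), so about 1 fall per week is a more suitable illustration than 3.5.

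**Conclusion.** The point holds as a minor one. SAP 14.6 and 24.1.10 leave PAMSys falls without a denominator, and a count over 2 weeks followed by a count over 4 weeks cannot express a change in fall frequency. At nominal lengths and full wear, an unchanged rate gives a count ratio of 2.0 and a true halving gives 1.0. The fall rates are assumptions, but the ratio does not depend on them. The distortion falls on within-patient change, and on the arm difference in change only where baseline rates differ. Partial wear could add to it by an amount the documents do not allow one to estimate.

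The consequences are limited. The endpoint is exploratory, its SAP analysis is descriptive, and its data come from an optional subset at US sites. A reader might infer that the trial's conclusions on falls are compromised. They are not: falls as a secondary endpoint come from the diary, which is already adjusted per day, and nothing here touches the primary or key secondary analysis.

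**What to change.** In SAP 24.1.10, define PAMSys falls in each interval as detected falls divided by days of valid wear (or the same rate expressed per 28 days worn). State what counts as a valid day, and give the amount of missing wear beyond which the period is set to missing. In SAP 14.6, base the descriptive summaries and the change from baseline on that rate. This mirrors the adjusted diary measure in 24.1.11.

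The cost is a sentence or two and one derived variable. No new data are needed: the system reports wear compliance (Protocol 10.2.1.10), and days used are already summarised under SAP section 12.

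Two related passages should be reconciled in the same edit. The 30-day wear instruction in Protocol 10.2.1.10 does not fit a 2-week baseline interval. SAP section 12 places intervals 2 and 3 at V10-V11 and V13-V14, whereas the study flow chart, and Panel 21 for the diary, use V11-V12 and V14-V15. The lengths are the same, so the arithmetic above is unaffected.

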15.1 Calibrating primary analysis

The final analysis will use all available data on all enrolled participants at baseline through 48-72 weeks. A success threshold is defined for the final analysis to maintain an overall alpha of 5% evaluated one-sided. The effect of Lu AF82422 will be evaluated using a Bayesian posterior probability of superiority relative to placebo with a threshold of 97.5% identified through simulations.

Lu AF82422, CCI dose: $Pr(\theta_2 < 1) > .975;$

15.2 Testing Strategy including Secondary Endpoint(s)

To protect the type I error for the primary analysis, i.e., analysis of UMSARS TS and the key secondary analysis, i.e., analysis of mUMSARS, both using the Bayesian progression model, a testing strategy will be applied. Firstly, both endpoints will be evaluated individually by applying the pre-defined threshold to the posterior probability for Lu AF82422 being superior to placebo, where the thresholds have been calibrated to be equivalent to the targeted 5% significance level evaluated one-sided. Following, the Fixed-Sequence Method will be applied evaluating the two prioritized analyses in a hierarchical manner:

- Step 1: UMSARS TS evaluated using the derived posterior probability (test equivalent to a one-sided 5% level). If significant,
- Step 2: mUMSARS evaluated using the derived posterior probability (test equivalent to a one-sided 5% level).

16 Safety

16.1 Adverse Events

16.1.1 General Methodology for Adverse Events

Unless otherwise specified, tables, graphs, and listings will be based on the APTS.

Tables by preferred term and tables by system organ class (SOC) and preferred term (PT) will be sorted in descending order based on the percentages of patients with these adverse events.

Unless otherwise specified, the summaries of adverse events will include the number and percentage of patients with an adverse event, and the total number of events.

In summaries of TEAEs by preferred term and intensity, and in summaries of causally related TEAEs by preferred term and intensity, the maximum intensity for the preferred term within an analysis phase will be used.

Listings of adverse events will be sorted by site, patient number, and adverse event start date, and will include preferred term, investigator term, adverse event start date, end date,, duration of the adverse event, date of death, action taken, causality, intensity, seriousness, and outcome. For adverse events that change in intensity, each intensity will be included.

16.1.2 Coding of Adverse Events

Adverse events will be coded using MedDRA, Version 26.0 or later.

16.1.3 Classification of Adverse Events

Adverse events will be classified according to the date of onset (or worsening of intensity/seriousness) of the adverse event and end date as follows:

- *pre-treatment adverse event* an adverse event that starts (or worsens) on or after the date the patient signed the *Informed Consent Form* and prior to the date and time of first dose of IMP
- *treatment-emergent adverse event* (TEAE) an adverse event that starts (or worsens) on or after the date of first dose of IMP

An adverse event is considered causally related to the use of the IMP when the causality assessment by the investigator is probable or possible.

Data handling of change in intensity or seriousness of adverse events is described in section 24.5.2.

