# 11.3 Recording Adverse Events

Adverse events (including pre-treatment adverse events after signing *Informed Consent Form*) must be recorded on an *Adverse Event Form*. In addition, if the adverse event fulfils the definition of an adverse event requiring additional data collection, a specific *Hypersensitivity Form* must be filled out (for further details on the content of the form, see Appendix IV). The investigator must provide information on the adverse event, preferably with a diagnosis, or at least with signs and symptoms; start and stop dates (and start and stop time if the adverse event lasts less than 24 hours or occurs on the day of IMP administration); intensity; causal

relationship to the IMP; action taken; and outcome. If the adverse event is not related to the IMP, an alternative aetiology must be recorded, if available. If the adverse event is an overdose, underdose, the nature of the overdose/underdose must be stated (for example, medication error, accidental overdose). Other medication errors for example, wrong technique of infusion, wrong infusion rate etc. should likewise be recorded. If the intensity changes during the course of the adverse event, this must be recorded on the *Adverse Event Intensity Log*.

If the adverse event is *serious*, this must be indicated on the *Adverse Event Form*. Furthermore, the investigator must fill out a *Serious Adverse Event Form* and report the SAE to Lundbeck immediately (within 24 hours) after becoming aware of it (see section 11.4).

If individual adverse events are later linked to a specific diagnosis, the diagnosis should be reported and linked to the previously reported adverse events.

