#### 17.10 Safety Analyses

#### 17.10.1 Analysis of Adverse Events

Adverse events will be classified according to the time of onset of the adverse event:

- pre-treatment adverse event an adverse event that starts on or after the date the patient signed the *Informed Consent Form* and prior to the date of first dose of IMP
- *treatment-emergent adverse event* an adverse event that starts or increases in intensity during or after administration of first dose of IMP

Adverse events, sorted by system organ class and preferred term, will be summarized by period and treatment group.

Data on adverse events related to systemic hypersensitivity reaction collected via the dedicated *Hypersensitivity Form* will likewise be summarized by period and treatment group.

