24.3 Assigning Adverse Events to Analysis Phases

Adverse events will be assigned to an analysis period as follows:

- Adverse events prior to treatment Records not classified as TEAEs will have APHASE= PRETREAT
- Adverse events in the double-blind period (DBP) all TEAEs with date of onset or worsening of intensity/seriousness after first dose of IMP in the DBP and until first dose of IMP in the OLE period (planned for Visit 1E – for patients entering the OLE) or the Safety Follow up visit for the DBP (SFU Visit 25 – for patients NOT entering the OLE) (assigned APHASE = DOUBLE BLIND).
- Adverse events in the Open-Label Extension period TEAEs with date of onset or worsening of intensity/seriousness after first dose of IMP in the OLE period (Visit 1E) and until the final Safety Follow up visit for the OLE (Visit 64E) (assigned APHASE = OLE).

If the start date is missing/incomplete and not eligible for imputation, the TEAE will be assigned to the DOUBLE BLIND phase.

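### SAP 16.1.3 overlaps on the first-dose day: an event starting before that day's infusion is both pre-treatment and treatment-emergent, and read literally it has no analysis phase

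*SAP*

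**What the plan says.** SAP 16.1.3 opens with a date-based principle: "Adverse events will be classified according to the date of onset (or worsening of intensity/seriousness"). Its two categories then use different boundaries. A pre-treatment event is one that starts or worsens from consent and "prior to the date and time of first dose of IMP". A TEAE is "an adverse event that starts (or worsens) on or after the date of first dose of IMP".

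Protocol 17.10.1 pairs the boundaries the other way round. Pre-treatment ends "prior to the date of first dose of IMP", and a TEAE is "an adverse event that starts or increases in intensity during or after administration of first dose of IMP".

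Phase assignment follows in SAP 24.3: "Records not classified as TEAEs will have APHASE= PRETREAT". SAP 16.1.4 and 24.3 then fill the double-blind phase with TEAEs whose onset or worsening comes after the first double-blind dose. SAP section 23, which lists departures from the protocol, mentions only the merging of four reporting periods into two.

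On data collection, Protocol 11.3 requires start and stop times when an event "occurs on the day of IMP administration", and Protocol 10.11 has the time of each administration recorded in the eCRF.

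**The concern.** The two SAP categories should divide the time axis without overlap or gap. They do not, and the hours affected are ones in which events can plausibly occur. Protocol 10.9 places the clinical ratings, blood sampling and CSF collection before IMP administration. Panel 2 footnote o requires baseline CSF sampling to be finished before the infusion. Panel 2 also has signs and symptoms present at baseline before IMP recorded on the Adverse Event Form.

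An event from one of these procedures that begins before the first infusion cannot be caused by the drug. Whether it appears in a TEAE table should follow from the plan and not from a programmer's choice. There is a secondary effect. Protocol 11.1.2 treats causality assessment as not relevant for pre-treatment events, so an event handled as pre-treatment at the site but as a TEAE in the analysis could reach the TEAE-by-causality table of SAP 16.1.6 without a causality value. SAP 24.5.2 gives defaults for missing intensity and seriousness, but none for causality.

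**Working it through.** The plan gives no figure to reproduce, so the check compares the definitions as sets of onset times. Let D be the calendar date of the first dose and T its date and time.

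- SAP pre-treatment: from consent, onset < T.
- SAP TEAE: onset date ≥ D.
- Protocol pre-treatment: from consent, onset date < D.
- Protocol TEAE: onset ≥ T (during or after administration).

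| Onset | SAP 16.1.3 | Protocol 17.10.1 |
|---|---|---|
| Day before D | pre-treatment only | pre-treatment only |
| On D, before T (say 09:00, infusion at 13:00) | both | neither |
| On D, at or after T | TEAE only | TEAE only |
| After D | TEAE only | TEAE only |

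The SAP overlap and the protocol gap are the same window: the hours of day D before the infusion.

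Next, the phase rules applied to a complete record in that window that does not worsen later:

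1. It meets the TEAE definition, so the residual rule in SAP 24.3 does not send it to the pre-treatment phase.
2. Its onset is before T, so it fails the condition in 16.1.4 and 24.3 that onset or worsening come after the first dose. It does not enter the double-blind phase.
3. It precedes any open-label dose, so the open-label phase does not apply.
4. The fallback rules in 24.3 and 24.4.4 cover missing or incomplete dates. This record has a complete date, so they do not apply.

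The result is a TEAE with no phase. An event that starts before T and worsens afterwards is not affected in the same way: its worsening is treatment-emergent under every definition.

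Size, conditional on the event being counted as a TEAE and on the patient having no other event with that preferred term:

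- one active-arm patient changes an incidence by 1/40 = 2.5 percentage points;
- one placebo patient changes it by 1/20 = 5 percentage points.

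If the phase rule is applied literally, the by-period tables do not gain the event at all.

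The documents give no frequency for such events. Purely as an assumption, if 2% to 10% of the 60 planned patients had one, that would be 0.02 × 60 = 1.2 to 0.10 × 60 = 6, so about 1 to 6 patients.

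**The case against.** The strongest reply is that the overlap is nearly harmless. Because the pre-treatment phase is a residual, no record can carry both phase labels. The opening sentence of 16.1.3 speaks of the date of onset, and on a purely date-based reading the SAP's TEAE rule is the exact complement of the protocol's pre-treatment rule. The time element in the pre-treatment bullet would then be a slip of wording. That is a fair reading of what may have been intended, but it is not what the bullets say. It would also leave the double-blind phase condition excluding the very event it classed as a TEAE.

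A reader might go further and infer that these events are certainly counted as TEAEs in both arms and blur the hypersensitivity and first-infusion results. The documents do not support that. TEAE summaries are by study period (SAP 16.1.6), and the double-blind period admits only onset or worsening after first dose. Protocol 11.1.3 limits hypersensitivity reactions to events during or after an infusion, so the investigator-reported category is not touched. Only the sponsor's preferred-term searches in SAP 16.1.11 could pick up such an event, and those are also presented by period.

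Other limits stand. Visits may be spread over two consecutive days with IMP on the second (Panel 2 footnote d; Protocol 9.4.2), and an event starting on the first of those days is pre-treatment under every wording. CSF sampling does not apply to patients with the listed contraindications. The safety analysis is descriptive, so no error rate is at stake.

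**Conclusion.** The inconsistency holds on the text. For onset on the first-dose day before the infusion, SAP 16.1.3 gives two answers, Protocol 17.10.1 gives none, and the SAP phase rules leave a TEAE unassigned. No other section settles it. Two programmers following the plan could produce different safety tables from the same data.

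What does not follow is a known inflation of TEAE rates. The direction depends on programming: the event is either counted although it preceded exposure, or lost from the by-period tables. The practical effect is limited to part of one day per patient and is probably small. The 2.5- and 5-point figures apply only to the first of these outcomes, and the range of 1 to 6 patients is an assumption. This is a minor point, worth correcting because it costs so little.

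The conclusion rests on reading the SAP's pre-treatment limit as a single timestamp, which is its natural meaning.

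**What to change.** Make four changes to the SAP before unblinding:

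1. In 16.1.3, define a TEAE as an event that starts or worsens at or after the date and time of first dose, and a pre-treatment event as one before that date and time. This agrees with Protocol 11.1.1, which describes pre-treatment signs and symptoms as starting before the first dose.
2. State that an event on the first-dose day with a missing start time is classified as a TEAE. This is consistent with 16.1.6, which already includes dosing-day TEAEs with missing start times, and with the approach to missing dates in 24.4.4.
3. Use the same boundary for entry to the double-blind phase in 16.1.4 and 24.3, so that every event falls in exactly one phase. Changing 16.1.3 alone would leave a third boundary in place.
4. List the difference from Protocol 17.10.1 in section 23.

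The cost is SAP wording and a matching line in the programming specification. No new data are needed, because event start times on dosing days and administration times are already collected.
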